#### 9.1.1. Estimands

##### 9.1.1.1. Primary Estimand

The estimand is defined by the following attributes:

##### Atopic Dermatitis:

Treatment condition: received treatment: PF-07038124 ointment 0.01%, 0.03% or vehicle, without the benefit of additional prohibited medications and regardless of treatment compliance.

Population: Participants with mild or moderate AD as defined by the inclusion and exclusion criteria.

Variables: Proportion of participants achieving IGA score of clear (0) or almost clear (1) and a reduction from baseline of  $\geq 2$  points at Week 12 and other binary endpoints.

##### Psoriasis:

Treatment condition: received treatment: PF-07038124 ointment 0.01%, 0.03%, 0.06% or vehicle, without the benefit of additional prohibited medications and regardless of treatment compliance.

Population: Participants with mild, moderate, or severe PsO as defined by the inclusion and exclusion criteria.

Variables: Proportion of participants with PGA score clear (0) or almost clear (1) and a reduction from baseline of  $\geq 2$  points at Week 12 and other binary endpoints.

Inter-current Events: A) Prohibited medication – response will be considered as failure for time points after start date of the event for participants who receive prohibited medication post-randomization. B) Withdrawal and all other events, except COVID-19 pandemic, leading to missing data will be treated similarly assuming that participants no longer receive

benefit from the study intervention and hence will be considered as failure. C) COVID-19 pandemic: if a participant misses a visit due to COVID-19, he/she will be excluded from the analysis for that visit; If a participant discontinues treatment or withdraws from the study due to COVID-19, he/she will be excluded from the analyses after the treatment discontinuation visit or study withdrawal visit, respectively. D) Inadequate compliance – participants data will be used as recorded.

Population level summary: The difference in success rates between each dose level and vehicle.

#### **9.1.1.2. Secondary Estimand**

All binary secondary endpoints estimands are similar to the primary endpoint.

The continuous endpoint estimand is defined by the following attributes:

##### **Atopic Dermatitis:**

Treatment condition: received treatment: PF-07038124 ointment 0.01%, 0.03% or vehicle, without the benefit of additional prohibited medications and regardless of treatment compliance.

Population: Participants with mild or moderate AD as defined by inclusion and exclusion criteria.

Variables: Percent change from baseline in EASI total score at all study visit time points specified in [SoA](#).

##### **Psoriasis:**

Treatment condition: received treatment: PF-07038124 ointment 0.01%, 0.03%, 0.06% or vehicle, without the benefit of additional prohibited medications and regardless of treatment compliance.

Population: Participants with mild, moderate, or severe PsO as defined by the inclusion and exclusion criteria.

Variables: Change from baseline in PASI total score at all study visit time points specified in [SoA](#).

Intercurrent events: A) Prohibited medication – all scores measured at time points after start date of the event for participants who receive prohibited medication post randomization will be excluded from the analysis and treated as missing scores. Missing scores will be imputed based on the assumption that participants do not benefit from the IP treatment.

B) Withdrawal and all other events leading to missing data, except COVID-19 pandemic, will be treated similarly assuming participants have efficacy values similar to control participants. C) COVID-19 pandemic: if a participant misses a visit due to COVID-19,

he/she will be excluded from the analysis for that visit; If a participant discontinues treatment or withdraws from the study due to COVID-19, he/she will be excluded from the analyses after the treatment discontinuation visit or study withdrawal visit, respectively. D) Inadequate compliance – participants data will be used as recorded.

Population-level summary: The mean difference between each dose level and vehicle.

### **9.1.2. Multiplicity Adjustment**

For each indication, the overall family wise Type I error rate will be controlled at the 1-sided 0.025 level using the Hochberg step up procedure.

## **9.2. Analysis Sets**

For purposes of analysis, the following analysis sets are defined:

Participant Analysis Set	Description
Full Analysis Set	All participants randomly assigned to study intervention who take at least 1 dose of study intervention.
Safety Analysis Set	All participants randomly assigned to study intervention who take at least 1 dose of study intervention. Participants will be analyzed according to the product they actually received.

Defined Analysis Set	Description
CCI	

## **9.3. Statistical Analyses**

The SAP will be developed and finalized before any analyses are performed and will describe the analyses and procedures for accounting for missing, unused, and spurious data. This section is a summary of the planned statistical analyses of the primary and secondary endpoints.

### **9.3.1. General Considerations**

Indication will be summarized separately by treatment.

### **9.3.2. Analyses for Binary Endpoints**

Analysis of primary binary endpoints is specified in [Section 9.3.4](#). Other binary endpoints at time points specified in the [SoA](#) will be analyzed similarly. No adjustments for multiplicity will be made for these endpoints.

### 9.3.3. Analyses for Continuous Endpoints

Analysis of secondary continuous endpoints is specified in [Section 9.3.5](#). Other continuous endpoints at time points specified in the [SoA](#) will be analyzed descriptively with no imputation. No adjustments for multiplicity will be made for these endpoints.

### 9.3.4. Primary Endpoint(s)/Estimand(s) Analysis

A landmark analysis of the composite IGA/PGA success endpoints at Week 12, defined in [Section 9.1.1.1](#), will be performed using the full analysis set. The proportions responding and the corresponding risk difference comparing active treatment arm to vehicle group will be analyzed using the unconditional exact method; the risk differences and the corresponding 2-sided unconditional exact 95% confidence intervals will be computed using Chan and Zhang (1999) method. The overall family wise Type I error rate will be controlled at the 1-sided 0.025 level using the Hochberg step up procedure.

In addition, Emax or other appropriate models may be used to characterize the dose response relationship. Details of the dose response model will be described in the SAP.

### 9.3.5. Secondary Endpoint(s)/Estimand(s) Analysis

Binary secondary endpoints will be analyzed similarly to the primary endpoints.

A landmark analysis of continuous endpoints including percent change from baseline in EASI and change from baseline in PASI at Week 12, defined in [Section 9.1.1.2](#), will be performed by ANCOVA using the full analysis set with baseline as a covariate. Missing data, except missing due to COVID-19 pandemic, will be imputed using a control-based method, assuming participants have efficacy values similar to vehicle participants, and data are MAR. The imputation will utilize ANCOVA model including baseline as a covariate. The analysis will combine the results from the multiple imputations using Rubin's rule's as implemented in SAS PROC MIANALYZE. MMRM models may also be used on observed data at all time points as sensitivity analyses. The fixed effects of treatment, visit, and treatment by visit interaction will be included. Baseline value will be included as a covariate. No adjustments for multiplicity will be made.

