### **5.2.2. Analyses for Continuous Endpoints**

Landmark (cross-sectional) analyses of key continuous endpoints will be performed by analysis of covariance (ANCOVA). The ANCOVA model will include treatment arm as fixed effect and baseline dependent variable as a covariate. Estimates of least square mean (LSM) values and the LSM differences between each PF-07038124 dose and vehicle will be derived. The corresponding p-values and 95% confidence intervals will also be presented.

Mixed model repeated measures (MMRM) models may be used when there are multiple time points. The fixed effects of treatment, visit, and treatment by visit interaction will be included. Baseline value will be included as a covariate. Unstructured covariance matrix will be assumed for the model errors when possible. Compound symmetry covariance matrix

will be used if the model with unstructured covariance doesn't converge. At each visit, estimates of least square mean (LSM) values and the LSM differences between each PF-07038124 dose and vehicle will be derived. The corresponding p-values and 95% confidence intervals will also be presented.

Unless stated otherwise, descriptive summary statistics of absolute values, change and percent from baseline for all continuous variables will be presented by treatment and time. These statistics will include n, mean, median, standard deviation, minimum and maximum.

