### **6.2.2. Continuous Secondary Endpoints**

Continuous secondary endpoints include percent CFB in EASI total score, CFB in PASI total score, and percent CFB in affected BSA.

- Estimand strategy: Secondary estimand ([Section 2.2.2](#)). This estimand is intended to provide an estimate of the treatment effect in the absence of prohibited medication use in a population that may or may not be fully compliant with the treatment.
- Analysis set: ITT Analysis Set ([Section 4](#)).
- Analysis methodology: A landmark analysis of these continuous endpoints at Week 12 will be performed by ANCOVA with baseline as a covariate. Missing data, except missing due to COVID-19 pandemic, will be imputed using a control-based imputation method. PROC MI will first be called to impute missing vehicle observations under the assumption data are missing at random (MAR) and impute

missing active treatment observations assuming they are similar to corresponding vehicle arm. The imputation will utilize ANCOVA model including baseline as a covariate fitted using only vehicle arm data. The analysis will combine the results from the multiple imputations using Rubin's rule's as implemented in SAS PROC MIANALYZE. MMRM models may also be used on observed data at all time points as sensitivity analyses. The fixed effects of treatment, visit, and treatment by visit interaction will be included. Baseline value will be included as a covariate. No adjustments for multiplicity will be made.

- Intercurrent events and missing data: A) Prohibited medication: all scores measured at time points after start date of the event for participants who receive prohibited medication post randomization will be excluded from the analysis and treated as missing scores. Missing scores will be imputed. B) Withdrawal and all other events leading to missing data, except COVID-19 pandemic: all missing scores will be imputed. C) COVID-19 pandemic: if a participant misses a visit due to COVID-19, he/she will be excluded from the analysis for that visit; If a participant discontinues treatment or withdraws from the study due to COVID-19, he/she will be excluded from the analyses after the treatment discontinuation visit or study withdrawal visit, respectively. D) Inadequate compliance – participants data will be used as recorded.

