### Sample SAS Code for Estimand 2 MMRM

```
proc mixed data=_dsnin order=internal alpha=<Value>;  
  by PARAMN;  
  class SUBJID AVISITN TRTPN;  
  model PCHG = BASE TRTPN AVISITN TRTPN*AVISITN /solution ddfm=kr;  
  repeated AVISITN/ participant =SUBJID type=un r rcorr;  
  /**try UN first, if not converged, will use CS***/  
  lsmeans TRTPN*AVISITN / diff cl alpha=<Value>;  
  ods output lsmeans=lsmeans diffs=diffs;  
run;  
/*For one-sided P-value calculation, the LOWER tail side should be used. */;
```

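### For PASI change, the optional sensitivity MMRM fits one baseline slope to all visits, so its Week 12 contrast may be only partly adjusted for baseline and can lose precision

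*Protocol*

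**What the plan says.** The main analysis of the continuous secondary endpoints is a landmark model (SAP 6.2.2): "A landmark analysis of these continuous endpoints at Week 12 will be performed by ANCOVA with baseline as a covariate". Its baseline slope therefore belongs to Week 12 alone. Missing values are filled by control-based multiple imputation: "The imputation will utilize ANCOVA model including baseline as a covariate fitted using only vehicle arm data".

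The MMRM is optional: "MMRM models may also be used on observed data at all time points as sensitivity analyses" (SAP 6.2.2, with the same provision in Protocol 9.3.5). Its mean model is given in Protocol 9.3.5: "The fixed effects of treatment, visit, and treatment by visit interaction will be included. Baseline value will be included as a covariate". SAP 5.2.2 has the same terms and adds the covariance: "Unstructured covariance matrix will be assumed for the model errors when possible", with compound symmetry as the fallback. The Appendix 4 code agrees: "model PCHG = BASE TRTPN AVISITN TRTPN*AVISITN /solution ddfm=kr". `BASE` enters once, and there is no `BASE*AVISITN`.

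The endpoints are on different scales (SAP 6.2.2): "Continuous secondary endpoints include percent CFB in EASI total score, CFB in PASI total score, and percent CFB in affected BSA". Only PASI is analysed as absolute change. The sample MMRM code models percent change. SAP Appendix 1 lists the MMRM as the one sensitivity analysis for EASI and PASI change.

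**The concern.** A participant cannot lose more PASI points than they had at baseline, so large losses are possible only from high baselines. Early in treatment little has changed and the slope of change on baseline is shallow. By Week 12 the plan expects half of an active arm to reach PASI-75, which means losing at least three quarters of the baseline score, so the slope should be much steeper. PsO entry spans PGA 2-4 and BSA 2-20% (Protocol 5.1.2.2), so baseline PASI is likely to vary widely.

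A single slope has to compromise across visits, and the likelihood tends to pull it towards the early, less variable ones. Week 12 is then under-adjusted for any chance difference in baseline PASI between arms.

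What is at stake is precision and interpretation. The MMRM is there to show how far the result depends on the imputation. That question is live, because SAP Section 4 and Table 1 exclude PGA/PASI ratings made at several visits by an unqualified rater in 10 PsO participants. If the two analyses also adjust for baseline differently, a gap between them has two possible causes.

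**Working it through.** **Plan's own figures.** The documents give no SD, slope, standard error or power for PASI change or for the MMRM. The nearest stated figures are the PsO powers with 30 per arm. The unconditional exact test gives 92.5% for PGA success (stated 92%) and 96.1% for PASI-75 (stated 96%). Both reproduce.

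**Formula.** Take complete data, n per arm, true Week 12 slope s12, fitted common slope b, baseline variance varB and Week 12 residual variance v.

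- Week 12 estimate = difference in mean change minus b x (difference in mean baseline).
- Error from under-adjustment = (s12 - b) x (difference in mean baseline). Its mean is zero under randomisation and its variance is (s12 - b)^2 x 2varB/n.
- Variance ratio against visit-specific slopes = 1 + (s12 - b)^2 x varB / v. This is never below 1, and it equals 1 when the slopes are equal.

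**Worked example.** Assumed: baseline SD 3.5, s12 = -0.60, b = -0.24, Week 12 residual SD 2, n = 30.

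- Variance ratio = 1 + 0.36^2 x 12.25 / 4 = 1.397, so the SE ratio is 1.18.
- In PASI points, the residual SE is 2 x sqrt(2/30) = 0.52 and the SD of the shift is 0.36 x 3.5 x sqrt(2/30) = 0.33.
- Simulation of this setting gave 0.619 against 0.538, a ratio of 1.15.

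**Range with complete data, from the formula.** Slopes are of change on baseline, first visit to Week 12, over several residual-SD and correlation patterns.

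| Slope pattern | SE ratio |
|---|---|
| Equal at all visits | 1.00 |
| Mild drift, -0.3 to -0.5 | 1.01-1.05 |
| Moderate drift, -0.1 to -0.5 | 1.05-1.20 |
| Strong drift, -0.1 to -0.625 | 1.09-1.33 |

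**Simulation of the planned analyses.** There were four arms of 30, seven visits and 300 runs per scenario. Assumed: baseline PASI mean 6 with CV 0.35-0.7, and mean Week 12 improvement of 75% active and 25% vehicle, chosen to give about 50% and 6% PASI-75.

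- The common slope was about -0.17 to -0.27, against a Week 12 slope of -0.57 to -0.61.
- The model-based SE ratio, common slope to visit-specific slopes, was 1.11-1.30. With weak or no drug effect it was 1.04-1.09.
- Empirical ratios were generally smaller. With complete data and the main assumptions the model-based ratio was 1.19 and the empirical 1.11. In one dropout scenario with lower between-visit correlation the empirical ratio was 0.99.
- With complete data, the MMRM with visit-specific slopes gave the same Week 12 estimate and SE as the ANCOVA (SE 0.505, against 0.600 with a common slope).

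**Against the control-based-imputation ANCOVA, with dropout** (active/vehicle; selected scenarios with the design effect):

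| Dropout | Reported SE ratio, MMRM/ANCOVA | Empirical SD ratio |
|---|---|---|
| 10/10% | 1.07 | 1.15 |
| 15/25% | 1.04 | 1.13 |
| 25/35% | 0.98 | 1.29 |

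Over all dropout scenarios the reported ratio ran from 0.95 to 1.15 and the empirical ratio from 1.08 to 1.29.

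**Stratification.** Neither simulation is reported as modelling the PGA strata. In the worked example, if PGA explained a quarter of baseline PASI variance, the SE ratio would be sqrt(1 + 0.75 x 0.397) = 1.14. If it explained half, sqrt(1 + 0.5 x 0.397) = 1.09. Both fractions are assumptions.

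**Percent change.** With improvement specified as a fraction of baseline, the slope of percent change on baseline stayed near zero at every visit and the SE ratio was 1.00.

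**The case against.** One baseline covariate is a valid MMRM, stated consistently in both documents. The analysis is optional, it concerns a secondary endpoint without multiplicity control, and no decision rule depends on it. The main ANCOVA already uses the Week 12 slope. Every figure for the size of the loss rests on SDs and slopes the documents do not give. PsO randomisation is stratified by PGA (Protocol 4.1), which shares thickening, colour and scaling with PASI and so limits the imbalance that drives the problem.

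All of this stands, and it makes the point a minor one. Stratification does not remove the problem: PASI also depends on the area involved, which is not a stratification factor, and PGA is not in the MMRM.

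A reader might infer four stronger conclusions, none of which the documents support:

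- *The MMRM is less precise than the ANCOVA it checks.* That holds with complete data if slopes differ. With dropout, the MMRM borrows from earlier visits and the Rubin's-rules SE is wide, so the reported SE can favour either. The two also make different missing-data assumptions. At 15/25% dropout the imputation pulls the ANCOVA estimate towards zero (-2.34 against -2.75), and estimate over SD is about 4.1 for the ANCOVA and 4.3 for the MMRM.
- *The Week 12 estimate is biased.* Randomisation keeps it essentially unbiased. The cost is noise tied to chance baseline imbalance.
- *EASI and BSA share the problem.* Both are percent changes, where the effect essentially vanishes.
- *The PCHG in the sample code means PASI will be modelled as percent change.* SAP 6.2.2 and Appendix 1 name change from baseline for PASI. The code is a sample that has not been adapted.

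**Conclusion.** The point holds for absolute change in PASI only, as a low-cost improvement to an optional sensitivity analysis. If the slope on baseline steepens over the visits, which is likely but not shown in the documents, the common-slope MMRM under-adjusts Week 12. With complete data its SE is then about 1-30% larger than with visit-specific slopes. The true loss is probably smaller because of PGA stratification, and it is nil if slopes are equal. Whether the reported SE exceeds that of the planned ANCOVA depends on dropout. The practical consequence is that an MMRM-ANCOVA difference cannot be read purely as the effect of missing-data handling. The main Week 12 ANCOVA and the primary IGA/PGA analysis are unaffected.

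**What to change.** - In Protocol 9.3.5, SAP 5.2.2 and SAP 6.2.2, extend the MMRM description to include baseline and the baseline-by-visit interaction.
- In the SAP Appendix 4 MMRM code, use `BASE TRTPN AVISITN TRTPN*AVISITN BASE*AVISITN` on the right-hand side of the model statement.
- In the same code, set the response to `CHG` for PASI and keep `PCHG` for EASI and BSA.

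The interaction adds one parameter for each visit after the first: with Weeks 1, 2, 4, 6, 8, 10 and 12, that is 7 - 1 = 6 degrees of freedom among about 120 PsO participants. No new data are needed. With complete data and unstructured covariance, the Week 12 MMRM contrast then matches the Week 12 ANCOVA, so a gap between them can be attributed more directly to the handling of missing data.

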### 9.3.6. Tertiary/Exploratory Endpoint(s)

Tertiary and exploratory endpoints will be analyzed descriptively. [CCI](#)

### 9.3.7. Safety Analyses

The safety data will be summarized in accordance with Pfizer Data Standards. All safety analyses will be performed on the safety population. Safety endpoints include Incidence of treatment emergent AEs and SAEs, clinically significant changes in vital signs, ECG, and laboratory tests.

### 9.3.7.1. Electrocardiogram Analyses

Changes from baseline for the ECG parameters QT interval, heart rate, QTc interval, PR interval, and QRS complex will be summarized by treatment and time.

The number (%) of participants with maximum post-dose QTc values and maximum increases from baseline in the following categories will be tabulated by treatment:

#### Safety QTc Assessment

Degree of Prolongation	Mild (msec)	Moderate (msec)	Severe (msec)
Absolute value	>450-480	>480-500	>500
Increase from baseline		30-60	>60

### 9.3.8. Other Analyses

CCI [REDACTED] data from Retained Research Samples may be collected during or after the trial and retained for future analyses; the results of such analyses are not planned to be included in the CSR.

CCI [REDACTED]

### 9.3.8.2. Interim Analyses

An interim analysis may be performed to assess efficacy and safety when approximately 60% of the planned participants, ie, approximately 25 participants per arm in AD and 18 participants per arm in PsO have completed or had the chance to complete Week 8 visit. Interim analysis results may be used for decisions regarding stopping for futility and internal program development. Additional interim analysis may be performed and will be detailed in the IRC charter.

Before any interim analysis is performed, the details of the objectives, decision criteria, dissemination plan, and method of maintaining the study blind as per Pfizer's SOPs will be documented and approved in an IRC charter. In addition, the analysis details will be documented and approved in the SAP.

## 9.4. Sample Size Determination

### 9.4.1. Sample Size Determination for AD

A sufficient number of participants will be screened to achieve approximately 120 participants randomly assigned to study intervention. The sample size calculation is based on the primary efficacy estimand IGA success at Week 12. Assuming 15% IGA

success rate for the vehicle arm, a sample size of 40 per arm will have 89% power to detect a treatment difference of 35% under a 1-sided Type 1 error 0.0125 for each of the 2 dose levels comparison to vehicle by the unconditional exact test, with an overall Type 1 error 0.025 1-sided. In addition, this sample size will provide 96% power to detect a 42% difference in EASI-75 between an active arm (62% EASI-75) and vehicle (20% EASI-75).

